Intra- and postoperative opioid consumption is another commonly studied outcome of acupuncture.^[13] In a randomized controlled trial (RCT) of 54 patients receiving THA, researchers randomized patients to receive either auricular (of the ear) or sham acupuncture treatment and compared the amount of piritramide (a synthetic opioid closely related to fentanyl and commonly used in European countries) used

intraoperatively.^[9] The results showed that patients in the acupuncture group required significantly less piritramide intraoperatively compared with sham (37 ± 18 mg vs. 54 ± 21 mg). A similarly constructed RCT also studied the effects of preoperative auricular acupuncture on intraoperative opioid use, but researchers instead studied fentanyl use and included patients undergoing TKA.^[14] These researchers, too, found that patients in the acupuncture group required significantly less opioid during surgery than patients in the sham acupuncture group (620.7 ± 258.2 μ g vs. 868.6 ± 319.3 μ g). Further, these patients on average lasted longer before requesting analgesia and exhibited lower visual pain scores. Several other studies have also demonstrated that preoperative acupuncture lessens the need for opioids during and after surgery.^[4,10,15,16] Reducing opioid consumption through the introduction of safely administered acupuncture poses a potential net improvement for patient safety and hospital costs.

Perhaps the most commonly cited benefit of acupuncture is increased relaxation and decreased anxiety, and several systematic reviews have reported that these benefits persist in the clinic.^[1,3,17] For patients with anxiety, depression, or other mental ailments, this is an important finding considering the substantial evidence linking poor mental health with significantly worse surgical outcomes.^[18-27] For example, one systematic review that accounted for 53,562 patients undergoing THA concluded that depression and anxiety were associated with increased postoperative pain, and another that accounted for 95,560 patients undergoing TKA found that the most consistent and significant indicator of dissatisfaction related to surgery was preoperative anxiety.^[27,28] Despite this evidence that poor preoperative mental health is detrimental to both practitioners and patients of surgery, there are currently no guidelines for improving preoperative mental health conditions.^[25]

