3.2 Randomization

Patients will be randomized immediately following the consenting process. Randomization will be achieved using a random number generator, which will randomly produce a 0, representing the Acupuncture group, or a 1, representing the Control group, for each patient. Patients will immediately be informed, for their convenience, of their group assignment given the non-blinded nature of the trial.

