4.0 CRITERIA FOR SUBJECT ELIGIBILITY

4.1. Subject Inclusion Criteria

- Female or male patients undergoing TKA or THA surgery at the Bone-and-Joint Institute at Hartford Hospital
- High-anxiety (APAIS-A-T >10)
- Age: 52 to 85

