For the primary aim *pain*, based on data from the first 31 patients enrolled, our sample size calculation indicates that a minimum of 26 subjects per group are needed using a repeated measures design (each subject is measured 4 times) with 2 groups for a total of 52 subjects. This design achieves 81% power to test factor B1 if a Geisser-Greenhouse Corrected F Test is used with a 5% significance level and the actual effect standard deviation is 0.255 (an effect size of 0.40319). We estimate an attrition rate of 10%, which will require 58 subjects; however we will aim to enroll 60 subjects (30 per group). For the second primary aim *anxiety*, we performed two sample size calculations. One based on the data of all 17 patients in the acupuncture group, and another excluding the 3 patients for which protocol deviations were reported due to methods collecting the anxiety measure. With all 17 patients, the difference in the response of anxiety from pre to post acupuncture was normally distributed with a standard deviation 26.27. If the true difference in the mean response of matched pairs is 35.64, we will need to study 6 pairs of subjects to be able to reject the null hypothesis that this response difference is zero with probability (power) 0.8. The Type I error probability associated with this test of this null hypothesis is 0.05. With the 3 patients removed, the difference in the response of anxiety from pre to post acupuncture was normally distributed with standard deviation 26.588. If the true difference in the mean response of matched pairs is 39.14, we will need to study 6 pairs of subjects to be able to reject the null hypothesis that this response difference is zero with probability (power) 0.8. The Type I error probability associated with this test of this null hypothesis is 0.05.

Pain is the more appropriate primary outcome of the two primary outcomes to base the sample size on because there are 4 time points of data for each group for this variable. The other primary outcome, *anxiety* does not have a post measure for the control group (per the study design), and therefore a within-group pre to post change in the acupuncture group is being performed to examine this outcome. We acknowledge that this within group design is weaker than the design to assess the pain outcome measure.

Statistical Methods

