Patient demographic and clinical (including operative) characteristics will be compared between groups using an independent samples t-test if continuous data are normally distributed), or Mann Whitney U if continuous data are not normally distributed. A chi-square or Fisher's exact test (if cell counts are <5) will be used to compare these characteristics between groups for categorical variables. All continuous variables will be expressed as mean±SD or median, IQR as appropriate. Categorical variables will be expressed as frequency (%).

The primary and secondary study outcomes will be compared between groups two ways. First, an independent samples t-test or Mann Whitney U test if deemed more appropriate for the scale data (which may be considered ordinal) will be used to compare outcomes at each time point between the two groups. Second, a mixed model for repeated measures will be used to compare the study outcomes that are repeated over time (e.g., Pain). This model was chosen instead of a repeated measures ANOVA due to the ordinal nature of the repeated outcome measures in addition to this test being more appropriate for non-normal residuals, missing data, as well as the ability to treat the time points as discrete categories or as true numbers, which accounts for any variability in when the measures are administered to patients.

We anticipate that the timing of the measures being administered may fluctuate slightly due to measures being taken PostOP.

All analyses will be conducted using SPSS version 26.0. P (2-sided) < .05 will be deemed the level of statistical significance.

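### Does pooling hip and knee replacements under unstratified randomisation mean that the pain comparison needs a term for the operated joint?

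*Combined protocol and SAP*

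**What the plan says.** Section 4.1 pools the two operations: "Female or male patients undergoing TKA or THA surgery at the Bone-and-Joint Institute at Hartford Hospital". Section 3.2 allocates by a "random number generator, which will randomly produce a 0, representing the Acupuncture group, or a 1, representing the Control group, for each patient" and names no stratification factor.

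In Section 11.0, Statistical Methods: "The primary and secondary study outcomes will be compared between groups two ways". The first way is a t-test or Mann-Whitney test at each time point. The second is the longitudinal model: "Second, a mixed model for repeated measures will be used to compare the study outcomes that are repeated over time (e.g., Pain". No terms are listed for that model, neither covariates nor the group and time effects it must contain. The same section has clinical characteristics, operative ones included, compared between the arms.

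Section 11.0, Sample Size, re-estimates the requirement for pain "based on data from the first 31 patients enrolled". It arrives at 26 per group, with four measurements each, for 81% power; "the actual effect standard deviation is 0.255 (an effect size of 0.40319". It then allows for 10% attrition, which gives 58; "however we will aim to enroll 60 subjects (30 per group".

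**The concern.** Hip and knee replacement are different operations, and it is plausible that pain in the recovery unit differs between them. The joint is fixed before randomisation and known for every patient, so it could be adjusted for at no data cost. The design does not balance it, and the stated analysis does not mention it. The pain study behind the original sample size covered knees only (in it, "researchers instead studied fentanyl use and included patients undergoing TKA"), whereas this trial also takes hips.

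If joint explains a good part of the variation in pain, an analysis without it leaves that part in the error term. A trial with 81% power at its minimum size has little precision to spare, so a free gain would be worth having.

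**Working it through.** **What kind of problem it could be.** Under simple randomisation the operated joint is independent of the arm. The unadjusted difference is therefore unbiased. An uneven split of knees between arms in a given trial is part of the sampling variation that the standard error measures. Simulation at N = 52 gave a type I error of 4.9% to 5.2% with and without a joint term. The only possible cost is power.

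**The plan's own figure.** Inputs from Section 11.0: N = 52, f = 0.40319, two-sided 5% level. For a between-patient factor, power comes from a noncentral F with 1 and N − 2 = 50 degrees of freedom and noncentrality N·f² = 52 × 0.40319² = 8.45. The result is 81.4%, against the stated 81%.

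**Power with a joint term.** Let R² be the share of the variance of a patient's mean pain that is due to joint. The noncentrality becomes N·f²/(1 − R²) × (1 − 1/(N − 1)), with N − 3 = 49 degrees of freedom. The last factor is the expected price of chance imbalance between arm and joint. R² is assumed, because the documents give no value.

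| R² | Noncentrality | Power | Change from 81.4% (points) |
|---|---|---|---|
| 0% | 8.29 | 80.6% | −0.8 |
| 2% | 8.46 | 81.3% | 0.0 |
| 5% | 8.72 | 82.5% | +1.2 |
| 10% | 9.21 | 84.5% | +3.1 |
| 15.6% | 9.82 | 86.7% | +5.3 |

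The term breaks even at about R² = 1/(N − 1) = 1/51 = 2%; below that it costs power. Simulation with one 0/1 draw per patient and a 50:50 joint mix agrees on the changes: 80.7% unadjusted, and 79.8% to 86.0% adjusted over the same range. With 54 evaluable (60 less 10%) the formula gives 82.8% unadjusted and 82.1% to 88.0% adjusted. With all 60 it gives 86.7%, and 86.1% to 91.2%.

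**What the upper end requires.** At a 50:50 mix (assumed), a hip-knee gap of D standard deviations contributes variance 0.25·D², so D = 2√R² = 2 × √0.156 = 0.79 SD. The treatment effect the trial is powered for is 2f = 2 × 0.40319 = 0.81 SD. The five-point gain thus supposes that joint moves pain about as much as acupuncture is hoped to.

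**More moderate assumptions.** Take a gap of 0.5 points and a correlation of 0.2 between the four ratings (both assumed). Then R² = 0.25 × 0.5² / (SD² × (1 + 3 × 0.2)/4) = 0.0625/(0.4·SD²). For a rating SD of 1.5, 2 and 2.5 this is 6.9%, 3.9% and 2.5%. With arms of 26, simulated power goes from 81.2% to 83.1%, 81.9% and 81.4%: a gain of 1.9, 0.7 and 0.2 points. If the gap is absent at the preoperative rating, its average over four ratings is 0.75 × 0.5 = 0.375. The shares are then 3.9%, 2.2% and 1.4%, and power is 81.9%, 81.3% and 81.0%: +0.7, +0.1 and −0.2 points. The 15.6% share comes out of this formula only at SD = 1 (0.0625/0.4 = 0.156).

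**The case for a change.** The best case for the term is that the stakes are lopsided: under one point lost if joint is irrelevant, about five gained at the top of the range, for a single model term. Larger shares would give more: at N = 52, about 7 points at 20% and 11 at 30%. The top of the range also has some link to the plan's figures. If 0.255 is in pain points, the SD of a patient's mean is 0.255/0.40319 = 0.632, and a half-point gap gives (0.25/0.632)² = 15.6%. Visible imbalance is quite likely too. With arms of 26 and an even joint mix, the difference in knee shares has standard deviation √(0.25 × 2/26) = 0.139, so a gap of 20 percentage points or more arises in about 15% of trials. A term fixed in advance would forestall an improvised adjustment.

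The arithmetic stands, and so does the remark that a fixed rule is better than an improvised one. The rest does not make a defect:

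- The plan does not state the unit of 0.255. If it is points, the treatment difference is 2 × 0.255 = 0.51 points, so the upper end still needs a joint effect as large as the treatment effect. No section says that hip and knee pain differ at all.
- The knee-only source no longer sets the sample size. The re-estimate uses this trial's own first 31 patients, recruited under criteria that admit both joints. Whatever hip-knee variation was present among them is already in the variance behind the 81%.
- Section 2.0 names preoperative pain as the most consistent predictor of postoperative pain, and Sections 7.1 and 7.2 collect it in both arms. If one covariate were to be chosen, the documents support that one. What joint would add beyond it is unknown.
- Section 11.0 lists no model terms, so it does not exclude joint. How fully the model is specified is a different and wider question.
- A joint term added now would be chosen after pain data from an open-label trial had been used, and one constant joint effect would not fit a gap that appears only after surgery.

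**Conclusion.** The concern does not hold. The planned pain comparison is valid without a joint term, and the documents do not show that adding one would help. The change at N = 52 runs from about −1 to +5 points for an assumed variance share of 0% to 15.6%. It is about −0.2 to +1.9 points for a half-point gap with assumed rating SDs of 1.5 to 2.5 and correlation 0.2. The range includes a loss.

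These figures rest on an assumed joint mix of 50:50 (other mixes, at the same share, change little), on the planning variance already including any joint variation, and on the between-group F test standing in for the mixed model. Good evidence of a large hip-knee difference in early pain would make the term worth having. As the documents stand, it is a matter of preference.
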